1.1. DISEASE BACKGROUND*

Diabetes has become a major health issue for many developed and developing countries. There are 347 million people affected by Diabetes globally, and this number is expected to increase to 366 million by 2030 (Wild et al. 2004). Among those affected by Diabetes, over 90% people are diagnosed with Type 2 Diabetes (T2DM) (World Health Organization 2015). There were 999,000 Australians (4.6%) reported to have diabetes in 2012, the majority (85.3%) of which were T2DM (Australian Bureau of Statistics 2012). The prevalence of diabetes in Australia is expected to grow to 3.5 million by 2033 (Magliano et al. 2009).

Diabetes mellitus is a chronic disease characterized by hyperglycaemia resulting from defects in insulin secretion, insulin function, or both. It significantly affects people's health and is associated with many complications, including damage to several organs, especially the eyes, kidneys, heart, nerves and blood vessels.

The treatment of T2DM involves achieving optimal blood glucose level and of other known risk factors that damage blood vessels or organs (Australia Bureau of Statistics 2012). The management can be very challenging (Wallace & Matthews 2004), as it requires medication and insulin use as well as lifestyle changes such as a healthy diet (Kastorini & Panagiotakos 2009; Rahati et al. 2014) and increased physical exercise (Anders & Schroeter 2015).

There is growing evidence indicating an association between vitamin D levels and T2DM, and the association between 25 (OH) D and insulin resistance is currently classified as evidence level II by the NMHRC (Nowson et al. 2012). A large observational study from Finland found that males with the highest serum vitamin D level had the lowest risk of developing diabetes (Knekt et al. 2008). A similar result was found in women in a nested case-control study (Pittas et al. 2010).

A randomised trial conducted among non-diabetic but insulin-resistant South Asian women in New Zealand indicated that there was a significant improvement in insulin resistance by supplementing with vitamin D (von Hurst, Stonehouse & Coad 2010). This study suggested the importance of keeping a good 25(OH)D level (50-80 nmol/l) as a long-term maintenance, as it can benefit both insulin resistance and insulin sensitivity however not the secretion. Another randomized clinical trial suggested that vitamin D slowed down the increase in fasting glucose that may benefit T2DM patients (Pittas et al. 2007).

In our recent published review (Yu et al. 2018), we had assessed the association between vitamin D and glycaemia control among T2DM patients from eligible sixteen Randomised Controlled Trials (RCTs) and had concluded that the current reviewed RCTs did not support the association, considering with study limitations we suggest that more large, long-term and better-designed RCTs using heterogeneous vitamin D sources are required in the future.

1.2. RATIONALE FOR PERFORMING THE STUDY*

The current study hypothesized that adequate vitamin D level will help with correcting blood sugar level and HbA1c. It is aimed to determine the prevalence of vitamin D deficiency among DM patients; whether DM patients have low vitamin D intake in daily life; and whether corrected vitamin D level will benefit DM patients. This study will help to understand and explain the possible association between vitamin D and Diabetes Mellitus, help to reduce the cost of clinical care; the cost of medicine; reduce the compliance of DM and reduce the incidence of hospitalization.

2. STUDY OBJECTIVES*

2.1. PRIMARY OBJECTIVE*

To determine the role of vitamin D (through vitamin D oral supplementation, sun exposure, dietary intervention compare to wait list control) in controlling and reducing DM risks (as measured by HbA1c).

2.2. SECONDARY OBJECTIVES

To determine the prevalence of vitamin D deficiency among T2DM patients and, To determine the differences of heterogeneous vitamin D sources and its impact on DM control.

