The vitamin D supplement group will be given an oral vitamin D supplement to ingest, dosage set as 500 IU per day. The dietary intervention group will be asked to follow a 'vitamin D food resources' list to obtain 10-15 μ g/d of vitamin D from food. The sun exposure group will be required to expose about 15% of body surface (hands, face and arms) to natural sunlight anytime from 10am to 4pm for 3-4 minutes/d from December to January, or 8 minutes/d from July to August or 10— 11 min/d from February to June or September to November, to get approximately 12.5 μ g/d of vitamin D per day. No interventions will be given to the wait list control group.

The total study period of the trial is 9 months. A face-to-face adherence reminder and examination session will occur at baseline and on a monthly basis. A blood test of vitamin D level and DM biomarkers will be obtained at baseline, and at the 3rd month and 9th month session. Participants who report with any side effects or upset symptoms will be assessed by study therapists and excluded from the trial once being confirmed.

Statistical considerations

Sample size calculation: By setting the significance level α =0.05, the power 1- β = 0.8 based on Campbell & Machin (1993) formula: m=(Z α + Z2 β)2{ π 1(1- π 1)+ π 2(1- π 2)}/ δ 2, (Z α + Z2 β)2 = 7.849, δ = π 2- π 1=0.7-0.35= 0.35; m=28. Therefore for the current study, the sample size of each group is calculated as at least 28, hence it requires at least 112 participants in total. With the consideration of a dropout rate 10%-20%, it is planned to recruit 31-34 participants per group with 123-134 participants in total.

Analysis plan: Data are expressed as means ± SDs. Initially, the Kolmogorov–Smirnov goodness-of-fit test will be used to assess the normal distribution of variables. Secondly, two-factor repeated-measures analysis of variance (ANOVA) will be used with Bonferroni correction in the current trial with time stages and

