4. PARTICIPANT SECTION

4.1. INCLUSION CRITERIA*

Participants eligible for the trial should comply with all of the following criteria:

1) Aged ≥ 18 years old; 2) Diagnosed with DM in the preceding 12 months, and not on diabetic medication or insulin treatment; 3) Serum 25OHD is between 28 nmol/l and 85 nmol/l and not on vitamin D supplements or any relevant medications; 4) Do not have thyroid diseases, liver impairment, renal failure, cancer, osteoporosis, dementia, mental diseases or taking relevant medications; 5) Not pregnant or breastfeeding women.

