4.2. EXCLUSION CRITERIA*

Participants are not eligible for the trial if they are:

1) Unable to give written informed consent or follow the instructions in current trial; 2) are already on vitamin D supplementation or relevant medications; 3) have liver impairment, renal failure (eGFR <50 ml/min), cancer, osteoporosis, dementia, mental disease, and thyroid diseases including hyperparathyroidism, hypercalcaemia, or taking any relevant medications; 4) are < 18 years old or are pregnant or breastfeeding women. 5) are vegen and can not ingest any animal product.

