5.4. RECRUITMENT AND SCREENING*

Trial information will be provided through website, flyer and local advertising. The trial will also be introduced to GPs and allied health professionals for cross-referral recruitment. Participants who express an interest through email, phone calls and personal attendance at clinics will be recruited. These include self-referred participants and participants who are referred by a GP or health professional. Diabetic patients' lists (name only) in both clinic centres will be used to contact for an EOI (expression of interest) as well. Responses to any inquiries about participation in the research study are to be answered by a phone that is manned during business hours and answered by voicemail at all other times. A research assistant will respond to each inquiry immediately, using a screening instrument to identify eligible participants and provide the following instructions.

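### The share deficient among participants is set partly by the 25OHD entry window, so it cannot serve as the prevalence of deficiency in T2DM patients that section 2.2 promises

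*Protocol*

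**What the plan says.** The first secondary objective in Protocol section 2.2 is "To determine the prevalence of vitamin D deficiency among T2DM patients". Section 1.2 states the same aim for a wider group: "It is aimed to determine the prevalence of vitamin D deficiency among DM patients".

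Entry is restricted on the same measurement. Section 4.1 (repeated in the Synopsis) requires "Serum 25OHD is between 28 nmol/l and 85 nmol/l and not on vitamin D supplements or any relevant medications", and section 4.2 again rules out people who "are already on vitamin D supplementation or relevant medications". Section 4.1 narrows the sample further to people "Diagnosed with DM in the preceding 12 months, and not on diabetic medication or insulin treatment".

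On when 25OHD is measured, the Synopsis says "A blood test of vitamin D level and DM biomarkers will be obtained at baseline, and at the 3rd month and 9th month session"; sections 5.2 and 5.1 list the same three blood tests. The flow chart in 5.1 puts the baseline assessment after randomisation, while the table in 5.2 puts the eligibility check before the initial visit. Section 5.4 has a research assistant answer inquiries "using a screening instrument to identify eligible participants and provide the following instructions", and the clinic patient lists used for contact hold names only. No section says that 25OHD values of ineligible people are recorded, counted or analysed. No section gives a cut-off for deficiency.

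**The concern.** A prevalence is a share of a defined population on either side of a cut-off. Here people are admitted or refused on the very variable that the cut-off is applied to. Both tails of the 25OHD distribution are removed before anyone is counted, and supplement users, whose 25OHD may differ from that of non-users, are removed as well. This is selection on the outcome, and a larger sample does not cure it.

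What is at stake is the meaning of a published figure. A percentage reported as the prevalence of deficiency in T2DM patients would partly restate the eligibility criteria, and a reader could not tell how far. The lower end of the scale suffers most, because values below 28 nmol/l cannot appear at entry however common they are in the clinics.

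**Working it through.** The protocol states no prevalence, precision or sample-size figure for this objective, so there is nothing of its own to reproduce. The point rests on logic; the arithmetic only shows the possible size.

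**Logic.**
1. The target in 2.2 is the share of T2DM patients below a cut-off c.
2. The people whose 25OHD the protocol says is collected are participants, all of whom must lie in 28-85 nmol/l at entry (4.1).
3. For any c at or below 28, the share among them is 0 whatever the true share. For c between 28 and 85, the share is that of a truncated distribution.

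**Inputs.** Window 28-85 nmol/l: section 4.1. Cut-off: not stated. The nearest figure is the 50-80 nmol/l that the background section (1.1) reports as a good level to maintain, so 50 is used, with 30 as a lower assumed value. Distribution: not stated. Assumed normal, with means 45, 50, 55 and 60 and SDs 18, 20 and 25 nmol/l.

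**Formulas**, with F the normal distribution function:
- true share = F(c)
- share in the window = [F(c) − F(28)] / [F(85) − F(28)]
- share outside the window = 1 − [F(85) − F(28)]

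**Worked case, mean 45, SD 25.** F(28) = 0.2483, F(30) = 0.2743, F(50) = 0.5793, F(85) = 0.9452, so the window holds 0.9452 − 0.2483 = 0.6969.
- Below 30: true 27.4%; in the window (0.2743 − 0.2483)/0.6969 = 3.7%.
- Below 50: true 57.9%; in the window (0.5793 − 0.2483)/0.6969 = 47.5%.
- Outside the window: 1 − 0.6969 = 30.3%.

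**Selected rows of the 12-point grid** (these include every extreme):

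| Mean, SD | <30 true | <30 window | <50 true | <50 window | Outside |
|---|---|---|---|---|---|
| 45, 18 | 20.2% | 3.7% | 60.9% | 53.7% | 18.6% |
| 45, 25 | 27.4% | 3.7% | 57.9% | 47.5% | 30.3% |
| 50, 20 | 15.9% | 2.8% | 50.0% | 44.2% | 17.6% |
| 55, 18 | 8.2% | 1.8% | 39.1% | 36.6% | 11.5% |
| 60, 18 | 4.8% | 1.1% | 28.9% | 28.6% | 12.0% |
| 60, 25 | 11.5% | 2.0% | 34.5% | 33.0% | 25.9% |

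Over the grid, the true share below 30 is 4.8-27.4% against 1.1-3.7% in the window. Below 50 it is 28.9-60.9% against 28.6-53.7%, and the window figure is lower by 0.3 to 10.4 points.

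**Wider assumptions.** With means 40-70 and SDs 15-30 (conditioned on positive values), the difference, window minus true, runs from −26 to about 0 points at a cut-off of 30, from −11 to +4 at 50, and from about 0 to +23 at 75. The sign therefore depends on the cut-off and the population.

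These figures cover the 25OHD window only. The protocol gives nothing from which to size the effect of excluding supplement users.

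**The case against.** The strongest defence is that the denominator is read from silence. Section 2.2 speaks of T2DM patients, not of randomised participants. Eligibility needs a 25OHD value, and 5.2 places that check before the initial visit, so some pre-entry values must exist. The population for a descriptive secondary objective is often left to the SAP, which is not at hand. What stands is that nothing in the protocol forbids an estimate from everyone screened. What does not stand is that an SAP could repair the plan by itself: it can choose a population and a cut-off, but it cannot supply values that the protocol does not say are collected or kept.

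A second objection is that the bias may be trivial. At 50 nmol/l with mean 60 and SD 18, 28.9% and 28.6% are practically the same. That is correct, and the large contrast at 30 comes from an assumed cut-off only 2 nmol/l above the entry limit. But near-agreement would be accidental and could not be recognised from the participants' data.

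Two stronger readings are tempting and should be resisted. A reader might infer that the trial necessarily understates deficiency; because both tails are cut, the documents fix no direction. A reader might also infer that the question in 1.2, "whether DM patients have low vitamin D intake in daily life", is distorted by the same mechanism. It is not: entry is not conditioned on measured dietary intake, and intake is not listed in 2.2. Excluding supplement users and vegans (4.2) is ordinary selection, not truncation on the outcome.

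**Conclusion.** The concern holds in a limited form. As written, the objective in 2.2 and the entry criteria in 4.1 and 4.2 do not fit together, and no other source of 25OHD data is described. The share deficient among participants describes the entry window and should not be called a prevalence in T2DM patients. That conclusion, and the zero below 28 nmol/l, need no distributional assumption.

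The size does need one. Under normality with mean 45-60 and SD 18-25 nmol/l, the understatement is about 4 to 24 points at a cut-off of 30 (4.8 − 1.1 = 3.7 to 27.4 − 3.7 = 23.7) and about 0 to 10 points at 50, with about 11-30% of patients outside the window. Other cut-offs or populations can reverse the sign.

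The primary HbA1c objective, the randomisation and the between-group comparison are unaffected. The restriction to untreated diabetes diagnosed within 12 months, and the use of DM in the criteria but T2DM in the objective, weaken representativeness further; they are separate from the truncation.

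**What to change.** Main change: in 2.2, replace the prevalence objective with a description of baseline 25OHD in randomised participants, reword the matching aim in 1.2, and make no prevalence claim for T2DM patients. This costs one line in each section and changes no visit, treatment or primary analysis. The price is a narrower claim.

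Alternative, if the investigators want to keep the question: retain the 25OHD results obtained to check eligibility, with suitable consent, and report the share below a stated cut-off among all screened diabetic patients with a result, giving numerator and denominator. This costs more than keeping a log. People ruled out for supplement use by the screening questions may never have a 25OHD test, and using ineligible people's data may need its own consent provision. The result should be described as coming from a volunteer and referral clinic sample that may under-represent supplement users, since even this would not be a population prevalence.

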3. STUDY DESIGN*

3.1. DESIGN*

The D4D trial is designed as a multi-centre, single-blind, randomized, parallel group, superiority study, to determine the role of vitamin D from the oral supplement, sun exposure and dietary invention in controlling and reducing DM risks. Randomisation will be performed as block randomisation with an equal ratio allocation through MINUM, a computer program that randomises and stratifys participants equally into the different arms of the study.

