3.4. NUMBER OF CENTRES

Participants are to be recruited primarily from the Earlwood Medical Centre (EMC), which is a community medical centre located in south central Sydney. Participants are also to be recruited from the Bangor Medical Centre located in south Sydney. All the following research visits including assessment and data collection will only be conducted in the Earlwood Medical Centre.

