5.7. RANDOMISATION PROCEDURE

Allocation: Sequence generation

Participants will be randomly assigned to one of four different groups with an equal ratio referring to the permuted block randomisation. The software randomisation package MINUM will be used for sequence generation. The block sizes will not be disclosed, to ensure concealment.

Allocation concealment mechanism

Allocation concealment will be ensured, as the centre will not release the randomisation code until

the participants have been recruited into the trial. The randomisation will be conducted by an independent investigator (not the research student) and send the sequence to study therapists who are only responsible for implementing the randomisation.

Implementation

All participants who give consent for participation, and who fulfil the inclusion criteria, will be randomized. An independent investigator (not the research student) will send the randomisation instruction to the study therapist who is not involved in recruitment or outcome assessment. Follow the randomisation instrument, eligible study therapist prepares closed envelopes with printed randomisation numbers and are available in both recruitment centres. For every randomisation number, the corresponding code for the intervention group will be found inside the envelope. Only the study therapist will open the envelope and will find the treatment to be conducted for this participant. The therapist then gives the information about treatment that allocated to the patient. The randomisation list will be stored in the two centres for the whole time period of study.

6.SAFETY*

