8. STATISTICAL CONSIDERATIONS*

By setting the significance level α =0.05, the power 1- β = 0.8 based on Campbell & Machin (1993) formula: m=(Z α + Z2 β)2{ π 1(1- π 1)+ π 2(1- π 2)}/ δ 2, (Z α + Z2 β)2 = 7.849, δ = π 2- π 1=0.7-0.35= 0.35; therefore m=28. Therefore the sample size for each group in the current study was calculated to be

at least 28, with at least 112 in total. With the consideration of a dropout rate 10%-20%, it is planned to recruit 123-134 participants in total hence 31-34 participants for each group.

Data are expressed as means ± SDs. Initially, the Kolmogorov–Smirnov goodness-of-fit test will be used to assess the normal distribution of the values. Secondly, two-factor repeated-measures analysis of variance (ANOVA) with a Bonferroni correction will be used in the current trial with time stages and interventions as factors. Tukey's post-hoc comparison will be applied to identify the differences between four intervention groups at 3 months and 9 months in the case of significant interaction finding in ANOVA. Thirdly, correlations between variables will be evaluated by using either a Pearson (r) (for data with normal distribution) or a Spearman (rs) (for data with no normal distribution) correlation. A p-value <0.05 is considered to be statistically significant. All statistical analyses will be computed using the Statistical Package for Social Science version 17 (SPSS, Chicago, IL, USA). Missing values are to be treated according to the last observation carried forward (LOCF) method and will be assessed via sensitivity analysis.

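### Section 3.1 says allocation is stratified, section 5.7 describes only permuted blocks and no factor is named; section 8 compares arms without a baseline covariate or any stratum term

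*Protocol*

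**What the plan says.** Section 3.1 announces block randomisation in equal ratio through MINUM, described as "a computer program that randomises and stratifys participants equally into the different arms of the study". Section 5.7, which sets out the procedure, says: "Participants will be randomly assigned to one of four different groups with an equal ratio referring to the permuted block randomisation". It adds: "The software randomisation package MINUM will be used for sequence generation". It mentions neither stratification nor a factor, and no other section names one.

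Section 3.4 gives two recruiting centres, Earlwood as the main one and a second: "Participants are also to be recruited from the Bangor Medical Centre located in south Sydney". Assessment is at one site: "All the following research visits including assessment and data collection will only be conducted in the Earlwood Medical Centre". Under 5.7, sealed envelopes are available at both recruiting centres.

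Section 8 specifies a two-factor repeated-measures ANOVA "with a Bonferroni correction will be used in the current trial with time stages and interventions as factors". If the interaction is significant, Tukey comparisons between the four groups follow at 3 and at 9 months. Section 2.1 makes HbA1c the measure for the primary objective. The synopsis places blood tests at baseline, month 3 and month 9.

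**The concern.** The two randomisation sections leave open whether there is one list or several, and what would separate them. This cannot wait for a later analysis document, because the lists must exist before the first participant is allocated.

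The analysis should also match the allocation. Stratifying on a prognostic factor removes between-arm variation in that factor. An analysis that ignores the factor still counts that variation as error, so its standard errors come out too large. Separately, a group comparison at one visit that ignores the same participant's baseline HbA1c discards information the trial already collects. With at least 28 per arm, the loss of precision matters.

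**Working it through.** **1. The plan's own figure.** Section 8 uses 7.849 × {0.35 × 0.65 + 0.70 × 0.30} / 0.35² = 7.849 × 0.4375 / 0.1225 = 28.03, which agrees with the stated 28 per group (112 in total). The point does not dispute this figure; it supplies the arm size used below.

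**2. The two schemes side by side.** Sections 3.1 and 5.7 agree on blocks, equal ratio and software. Only 3.1 speaks of stratifying, and neither names a factor.

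**3. What omitting a stratum does.** This was checked by simulation under the null hypothesis, with 6,000 runs per setting. Taken from the protocol: 112 participants in four equal arms. Assumed, because the protocol gives no values: blocks of 8, two strata with one holding 20% or 50% of participants, and within-person correlation 0.6. The analysis had no stratum term. It was run on the 9-month change from baseline (the time-by-group contrast) and on the 9-month value alone. The Monte Carlo standard error at a true rate of 0.05 is √(0.05 × 0.95 / 6000) = 0.0028.

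| Allocation | Stratum effect | Type I error, change | Type I error, 9-month value | Model SE / true SE, change |
|---|---|---|---|---|
| Plain blocks | all settings | 0.047-0.055 | 0.044-0.054 | 0.985-1.007 |
| Stratified | none | 0.049-0.051 | 0.049-0.051 | 0.988-0.990 |
| Stratified | 20% of variance of level, constant over time | 0.046-0.051 | 0.021-0.022 | 0.979-1.005 |
| Stratified | 5% of variance of change | 0.043-0.046 | 0.044-0.045 | 1.022-1.027 |
| Stratified | 10% of variance of change | 0.033-0.038 | 0.034-0.036 | 1.043-1.063 |
| Stratified | 20% of variance of change | 0.021-0.023 | 0.026-0.028 | 1.091-1.112 |

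Plain blocks give correct standard errors. Omitting a stratum makes the test conservative and never liberal. A stratum effect that is constant over time cancels from the change contrast, but it does affect a single-visit comparison.

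**4. What a baseline covariate gains.** Let ρ be the correlation between baseline and follow-up HbA1c, with equal variances. The protocol gives no value, so the range 0.5-0.8 is assumed. The error variances, in units of SD², are:
- single-visit value: 1
- change from baseline: 2(1 − ρ)
- baseline as covariate: 1 − ρ²

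The standard error with the covariate, relative to a single-visit contrast, is √(1 − ρ²). This is 0.866 at ρ = 0.5 and 0.600 at ρ = 0.8, a cut of 13% to 40%. Relative to a change contrast it is √((1 + ρ)/2). This is 0.866 at ρ = 0.5 and 0.949 at ρ = 0.8, a cut of 13% to 5%.

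At 28 per arm the single-visit standard error is √(2/28) = 0.267 SD. With the covariate it is 0.231 SD (ρ = 0.5) or 0.160 SD (ρ = 0.8). The change contrast has 0.267 SD and 0.169 SD respectively.

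**The case against.** The strongest defence is that 3.1 and 5.7 agree on method, ratio and software. The remark about stratifying is a clause describing the program and may be loose wording for equal allocation. That is plausible, although 3.1 has already stated the equal ratio, so on that reading the clause adds nothing. It makes the point an ambiguity and not a firm contradiction.

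Second, baseline is one of the three blood-test times and most naturally enters as a level of time, so the interaction already compares change from baseline. This stands: the model does not ignore baseline. What is missing is a baseline covariate, and the follow-up comparisons are stated for single visits.

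Third, covariates are commonly left to a statistical analysis plan, which is not at hand. That is fair for detail, but section 8 does name the model and its factors, so it fixes something that can be improved. The case for a centre term is also weaker than usual, because all assessments take place at one site.

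A reader might go further and infer that either balance fails or the standard errors are wrong. The documents do not support this. Plain permuted blocks keep the arm sizes balanced, leave only chance differences in covariates, and give valid standard errors. A reader might also point to baseline 25OHD, since eligibility requires "Serum 25OHD is between 28 nmol/l and 85 nmol/l". With 31 per arm and an assumed 40% below 50 nmol/l, a gap of more than 15 percentage points from the wait list has a chance of about 24% for one active arm and 51% for at least one of three. That is ordinary sampling variation, already allowed for in the unadjusted standard errors, and the 40% is not a figure from the protocol.

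**Conclusion.** The point holds as an unresolved statement of the randomisation scheme together with an analysis that is less precise than it could be at almost no cost. It is not an error that invalidates the trial's inference. The mismatch between 3.1 and 5.7 alone needs only a clarification.

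If allocation is stratified and the factor is omitted, standard errors for change are about 2%, 5% and 10% too large when the factor explains 5%, 10% and 20% of its variance. They are unaffected if the factor acts only on a constant level. These shares are assumptions, because the protocol gives no prognostic strength for any factor. A larger inflation of 5-20%, from 1/√(1 − R²) with R² of 0.10-0.30 in HbA1c level, might be inferred. It does not carry over to the time-by-group test, where a constant effect cancels.

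The more useful gain comes from the baseline covariate: 13-40% off the standard error of a single-visit contrast and 5-13% off that of a change contrast, for an assumed correlation of 0.5-0.8.

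**What to change.** **Randomisation.** State one scheme in identical words in 3.1 and 5.7. Either delete the reference to stratifying or name the factor. Recruiting centre is the cheap choice, since envelopes are already held at both centres; it means two blocked lists instead of one. Stratifying on 25OHD at 50 nmol/l is optional and corrects no error.

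**Analysis.** In section 8, compare the arms at 3 and 9 months with baseline HbA1c as a covariate, and include any factor actually used to stratify. With baseline as a covariate, the repeated outcome consists of the 3- and 9-month values. The time-by-group interaction then tests only whether the arm differences change between those visits. The condition for the follow-up comparisons must therefore be reworded to rest on the group effect.

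**Cost.** A few sentences in three sections, settled before the first allocation, and at most one additional list. No extra visits, samples or participants are needed.
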